## 8.2 Discussion of Study Design, Including Choice of Control Group

The proposed study design is standard for first in human oncology trials assessing safety and tolerability. Neither a placebo nor an active control will be included in this study.

## 8.3 Selection of Study Population

### 8.3.1 Inclusion Criteria

Individuals eligible to participate in either part of the Phase I Part A (Dose Escalation) or Part B (Dose Expansion) and the Phase II portion of the study must meet all of the following criteria:

1. Age  $\geq$  18 years, including males and females.
2. Subject is willing and able to participate and comply with all trial requirements and to provide signed and dated informed consent prior to initiation of any trial procedures.
3. Subject has histologically or cytologically confirmed locally advanced or metastatic breast cancer for which standard curative measures do not exist.
4. Tumor must be HR-positive and HER2-negative as determined in the most recently obtained archival tumor tissue sample from a metastatic site (unless de novo diagnosis or no metastatic biopsy undertaken) using locally accepted criteria by the local pathology report. HR positive is defined as ER+/PR+, ER+/PR-, ER-/PR+.
6. The subject must have received at least 1 prior hormonal regimen for locally advanced or metastatic disease.
7. Subject must have received at least 6 months of a prior continuous endocrine therapy for locally advanced or metastatic breast cancer.
8. Subject has a life expectancy  $\geq$  6 months in the opinion of the investigator.
9. Subject has an Eastern Cooperative Oncology Group (ECOG) Performance Status (PS) of 0 or 1.
10. Females of childbearing potential must be willing to adhere to highly-effective contraception during the study and for 90 days following the last study drug administration:
  - a. Highly effective contraception methods must include one of the following:
    - i. Total abstinence (when this is in line with the preferred and usual lifestyle of the subject. Periodic abstinence (eg, calendar, ovulation,

symptothermal, post-ovulation methods) and withdrawal are not acceptable methods of contraception.

- ii. Female sterilization (have had surgical bilateral oophorectomy with or without hysterectomy) or total hysterectomy or tubal ligation at least 6 weeks before taking study treatment. In the case of oophorectomy alone, only when the reproductive status of the woman has been confirmed by follow up hormone level assessment.
  - iii. Male partner sterilization (at least 6 months prior to screening). For female subjects on the study, the vasectomized male partner should be the sole partner for that subject and the success of the vasectomy must be medically confirmed as per local practice.
  - iv. Placement of a nonhormonal intrauterine device (IUD).
  - b. Additionally, females of childbearing potential, must meet all the following criteria:
    - i. Not pregnant, as confirmed by a negative serum pregnancy test ( $\beta$ -human chorionic gonadotropin) before starting study treatment.
    - ii. Not breastfeeding.
  - c. A female subject is considered to be of childbearing potential unless she meets one of the following criteria:
    - i. Is aged  $\geq 60$  years.
    - ii. Has had a hysterectomy, bilateral tubal ligation, or bilateral oophorectomy.
    - iii. Has medically documented ovarian failure (with serum estradiol and follicle-stimulating hormone levels).
    - iv. Is menopausal (amenorrhea  $\geq 12$  months) while off drugs that interfere with ovarian function.
11. Male subject must be willing to adhere to highly-effective contraception during the study and for 90 days following the last study drug administration. Highly-effective contraception methods must include one of the following criteria:
- a. Successful vasectomy.
  - b. For subjects who have not had a successful vasectomy, and are partners of women of childbearing potential, their partners adhere to any one of the following.
    - i. Hormonal contraception + male subject's use of a condom with spermicide.

- ii. IUD (hormonal or non-hormonal).
  - iii. Bilateral tubal ligation + male subject's use of a condom with spermicide.
  - iv. Depo Provera + male subject's use of a condom with spermicide.
12. Pre and peri-menopausal female subjects must be willing to take a LHRH agonist  $\geq 2$  weeks before the first study drug administration and for the duration of the study.
  13. Subjects must have not taken proton pump inhibitors (PPI) for 7 days prior to first study drug administration and agree to avoid taking PPI therapy for at least the first 2 cycles of therapy.
  14. Subjects must have a corrected QT interval (QTcF)  $< 470$  msec for females and  $< 450$  msec for males (as calculated by the Fridericia correction formula).
  15. Subjects must not have received prior hormonal therapy (including fulvestrant), CDK4/6 inhibitors, alpelisib, everolimus, or poly-ADP ribose polymerase (PARP) inhibitors within 2 weeks prior to the first administration of study drug.
  16. Subjects must not have received prior chemotherapy within 2 weeks or investigational therapy within 4 weeks prior to the first administration of study drug or within 5 half lives of either chemotherapy or investigational agent (whichever is earlier). Subjects must not have received antibody therapy within 4 weeks prior to first administration of study drug.
  17. Prior radiotherapy must have been completed at least 2 weeks prior to start of Cycle 1 with recovery of any toxicities to  $\leq$  Grade 1 (except for alopecia).
  18. Subjects must have had at least 4 weeks from major surgery.
  19. Subjects must have had any toxicities from prior therapy resolved or be  $\leq$  Grade 1 as defined by NCI-CTCAE, v 5.0 at the time of starting study treatment with the exception of alopecia.
  20. Subjects have the following laboratory values obtained  $\leq 28$  days prior to first dose (NOTE: if performed more than 3 days before the first study drug dose, then these laboratory tests need to be repeated within 3 days of C1D1 or pre-dose on C1D1 to ensure ongoing eligibility - with the exception of coagulation tests):
    - a. Serum creatinine  $\leq$  the upper limit of normal (ULN) or has an estimated glomerular filtration rate (eGFR)  $\geq 30$  mL/min/1.73 m^2 according to the Modification of Diet in Renal Disease (MDRD) formula.
    - b. Total bilirubin  $\leq 1.5 \times$  ULN unless prior history of Gilbert's syndrome.
    - c. Aspartate transaminase and alanine transaminase  $\leq 2.5 \times$  ULN, or  $\leq 5 \times$  ULN if due to liver involvement by tumor.
    - d. Hemoglobin  $\geq 9.0$  g/dL without requirement for red blood cell (RBC) transfusion within the last 4 weeks.

- e. Platelets  $\geq 100 \times 10^9$  cells/L.
- f. Absolute neutrophil count (ANC)  $\geq 1.5 \times 10^9$  cells/L (without the use of hematopoietic growth factors within the prior 3 weeks).
- g. Prothrombin time (PT) and INR  $\leq 1.5 \times$  ULN, activated partial thromboplastin time (PTT)  $\leq 1.5 \times$  ULN. If on chronic anticoagulation, the INR must be in the therapeutic range.

***Additionally, for individuals eligible to participate in Part A (Dose Escalation) of the Phase I portion of the study:***

- 21. The subject must have received no more than 2 prior chemotherapy regimens for locally advanced or metastatic disease.
- 22. Subjects must have evaluable disease. Subjects with both measurable and non-measurable disease are eligible.

***Additionally, for individuals eligible to participate in Part B (Dose Expansion) of the Phase I portion of the study and in the Phase II portion:***

- 23. Subjects must have measurable disease by RECIST 1.1 criteria
- 24. The subject must have received no more than 1 prior chemotherapy regimen for locally advanced or metastatic disease.
- 25. The subject must have had at least 1 and no more than 4 prior hormonal-based therapies for locally advanced, recurrent, or metastatic disease.
- 26. Subjects with brain metastases are eligible for the study (Phase I Part A, Phase I Part B, and Phase II Cohort C) if they meet all the following criteria:
  - a. The subject's brain metastases have been treated or do not require urgent local treatment at the time of study enrollment.
  - b. The subject has been off dexamethasone or is on a stable dose of dexamethasone of  $\leq 2$  mg daily (or an alternate steroid dosed at a level equal to  $\leq 2$  mg daily) for at least 2 weeks prior to first study drug administration.

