***Phase II Cohort B (non-measurable [evaluable] disease without evidence of CNS metastases):***

- 29. Subjects must have non-measurable and evaluable disease.
- 30. Subject must not have evidence of CNS metastases. (Imaging of the brain is NOT required if the subject does not have symptoms suggesting CNS disease.)

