***Additionally, for individuals eligible to participate in the Phase II Cohort C (CNS cohort)***

31. The subject must have received no more than 3 prior chemotherapy regimens for locally advanced or metastatic disease.
32. The subject must have had at least one prior hormone-based therapy for locally advanced, recurrent, or metastatic disease.
33. Subjects must have evaluable disease. (Subjects with either measurable or non-measurable disease are eligible.)

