### 11.1 Analysis Set

#### 11.1.1 Enrolled Analysis Set

The enrolled analysis set includes all subjects who enrolled into the study after signing an ICF and satisfying inclusion/exclusion criteria.

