9.2 Protocol Deviations

Important protocol deviations (IPD) are a subset of protocol deviations that may significantly impact the completeness, accuracy, and/or reliability of the study data or that may significantly affect a subject's rights, safety, or well-being and will be identified before database lock. Important protocol deviations may include, but are not limited to:

- Enrolled subjects who did not satisfy selected inclusion and exclusion criteria.
- Enrolled subjects who developed withdrawal criteria during the study but were not withdrawn.
- Subjects who received the incorrect dose.
- Subjects who received a prohibited medication.

Important protocol deviations will be summarized by deviation category.

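### Criterion 23 requires measurable disease throughout Phase II, so Cohort B (non-measurable disease) cannot enrol anyone as written, and Cohort C's own criteria have no effect

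*Protocol*

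**What the plan says.** Protocol 8.3.1 opens with a cumulative rule: individuals for Phase I and "the Phase II portion of the study must meet all of the following criteria". The same rule opens the synopsis list.

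Criteria 23 to 26 follow a heading that covers Part B "of the Phase I portion of the study and in the Phase II portion", with no cohort exception. Under it stand:

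- criterion 23: "23. Subjects must have measurable disease by RECIST 1.1 criteria";
- criterion 24: "The subject must have received no more than 1 prior chemotherapy regimen for locally advanced or metastatic disease";
- criterion 25: between 1 and 4 prior hormonal-based therapies.

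Cohort-specific lists come next. For Cohort A, criterion 27 repeats the measurable-disease requirement. For Cohort B, criterion 29 says "Subjects must have non-measurable and evaluable disease". The Cohort C list is headed *Additionally*. Its criterion 31 says "The subject must have received no more than 3 prior chemotherapy regimens for locally advanced or metastatic disease"; criterion 32 asks for at least one hormonal therapy with no upper limit; criterion 33 accepts either measurable or non-measurable disease. The synopsis has the same headings and numbering.

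Protocol 11.4.3 describes the Cohort B population as subjects without measurable disease and limits it to 15. The Enrolled Analysis Set (Protocol 11.1.1, matched by SAP 8.1) is "all subjects who enrolled into the study after signing an ICF and satisfying inclusion/exclusion criteria". SAP 9.2 gives, among examples of what important deviations may include, "Enrolled subjects who did not satisfy selected inclusion and exclusion criteria".

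**The concern.** One eligibility rule demands measurable disease of every Phase II subject, while one of the three Phase II cohorts is defined by its absence. Protocol 10.1 lets a site proceed to enrolment only when all inclusion and exclusion criteria are met, so literal compliance leaves Cohort B empty. Protocol 11.4.3 explains that subjects without measurable disease are enrolled so that Phase II resembles the general ER+ population, many of whom have bone-only disease. That purpose depends on the cohort enrolling.

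If sites instead follow what was plainly meant, every Cohort B subject enters against a written criterion. For Cohort C, sites have to guess whether a candidate with 2 or 3 prior chemotherapy regimens, more than 4 hormonal therapies, or only non-measurable disease is eligible. Different guesses would give a mixed population in a cohort of about 15.

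**Working it through.** This is a question of eligibility logic; the only arithmetic is counting.

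**Planned total.** SAP 5.3 splits Phase II into 50 (A), 15 (B) and 15 (C): 50 + 15 + 15 = 80. This reproduces the 80 evaluable subjects in Protocol 8.9 and SAP section 4. The synopsis and Protocol 8.1 and 8.6 call 88 the evaluable number, while also giving 88 as the ceiling after replacement; 80 is used here because it equals the sum of the cohorts.

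**Cohort B.** Criterion 23 requires measurable disease; criterion 29 requires non-measurable disease; both must hold.

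- Measurable disease present: 23 met, 29 failed.
- Measurable disease absent: 23 failed, 29 met.

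The eligible set is empty. Criterion 29 could be stretched to admit subjects with both kinds of lesion, but the cohort title and the description in Protocol 11.4.3 rule that out. The share lost is 15/80 = 18.75%, about 19%, and the reachable total is 50 + 0 + 15 = 65. With 88 as denominator the share would be 15/88 = 17%.

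**Cohort C.** Applying both lists together gives:

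| Item | Criteria 23-25 | Criteria 31-33 | Both together |
|---|---|---|---|
| Prior chemotherapy regimens | at most 1 | at most 3 | at most 1 |
| Prior hormonal therapies | 1 to 4 | at least 1 | 1 to 4 |
| Disease | measurable | either type | measurable |

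In each row the limits are nested and the stricter one binds. The last column equals the first, so 31-33 change nothing. The cohort is not empty; it is confined to a narrower group than its own criteria describe.

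**Cohort A and precision.** Criterion 27 repeats 23, so re-scoping 23 leaves Cohort A unchanged. The largest half-width of an exact (Clopper-Pearson) 95% interval over all possible counts is 14.5 percentage points at n = 50, which reproduces the plan's ±15%, and it is the same before and after the change.

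**Analysis sets.** The safety set is defined by dosing, and the efficacy set by one cycle of treatment plus a post-baseline tumour assessment. The clinical-benefit set is a subset of the efficacy set. None refers to eligibility; only the Enrolled Analysis Set does.

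**The case against.** The strongest reply is that the intent is clear. Cohort B is described as non-measurable disease throughout the protocol and SAP. Criterion 27 would be redundant if 23 were meant to govern all of Phase II. The heading above 23-26 is visibly loose, since criterion 26 sits under it yet names Phase I Part A, which the heading does not cover. Under Protocol 8.6 enrolment and cohort assignment are managed centrally, so an empty Cohort B is a result of the literal text and not a likely operational outcome. This stands as a forecast of what sites would do. It does not remove the contradiction: no section exempts Cohort B from criterion 23, and eligibility and deviations are judged against the written criteria.

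Three stronger readings are tempting, and the documents do not support them.

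- A reader might infer that Cohorts B and C are both blocked, up to 30 of 80 subjects (37.5%). That assumes every Cohort C subject would breach 23, 24 or 25. The documents give no such distribution, and the Cohort C limits are nested, not mutually exclusive.
- A reader might infer that Cohort B subjects would automatically become important deviations or be withdrawn. SAP 9.2 is conditional: it says what such deviations may include and refers to selected criteria. In Protocol 8.3.3, failing the entry criteria is a reason for which a subject may be withdrawn, not must be.
- A reader might infer damage to the efficacy estimates. Leaving the Enrolled Analysis Set alters a disposition count. Response rate excludes subjects without measurable disease and Cohort C, and Protocol 11.4.3 calls B and C exploratory.

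**Conclusion.** The concern holds for Cohort B: criteria 23 and 29 exclude each other, so a planned cohort of about 15 (19% of 80) cannot enrol under the text as it stands, and at most 65 Phase II subjects can. This rests on the cumulative rule that opens 8.3.1 and on Cohort B meaning subjects without measurable disease, as Protocol 11.4.3 says.

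For Cohort C the defect is ambiguous scope. Criteria 31-33 were evidently meant to widen entry but have no effect if 23-25 also apply. The number of subjects affected cannot be derived from the documents.

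If sites follow the intent, the consequence for Cohort B is a failed written criterion, exclusion from the Enrolled Analysis Set as defined, and possible flagging as important deviations. The primary response-rate analysis and the definitions of the safety, efficacy and clinical-benefit sets are untouched. If sites follow the letter, the Phase II clinical-benefit population without CNS metastases loses its planned Cohort B contribution, 15 of 65 (23%). SAP 6.1 pools Phase I subjects at the same doses, so the share of the pooled analysis would be smaller.

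**What to change.** Amend the eligibility text identically in Protocol 8.3.1 and the synopsis:

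- re-scope criterion 23 so that it does not reach Cohort B; criterion 27 already secures measurable disease in Cohort A;
- state which Phase II cohorts criteria 24 and 25 cover, including whether they bind Cohort B;
- reconcile 23-25 with 31-33 by stating whether the Cohort C criteria replace the general ones or add to them.

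The documents do not settle which prior-therapy limits should apply to Cohorts B and C; that choice is the sponsor's. Criterion 26 should be moved or its heading widened in the same edit, since it names Part A under a heading that does not.

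The cost is a wording amendment in two places. Sample size, Cohort A precision and the analysis-set definitions stay as they are. If Cohort B or C subjects have already entered, the sponsor should also record how criteria 23-25 were applied to them and whether they count in the Enrolled Analysis Set.

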***Phase II Cohort A (measurable disease without evidence of CNS metastases):***

- 27. Subjects must have measurable disease by RECIST 1.1 criteria.
- 28. Subject must not have evidence of CNS metastases. (Imaging of the brain is NOT required if the subject does not have symptoms suggesting CNS disease.)

***Phase II Cohort B (non-measurable [evaluable] disease without evidence of CNS metastases):***

- 29. Subjects must have non-measurable and evaluable disease.
- 30. Subject must not have evidence of CNS metastases. (Imaging of the brain is NOT required if the subject does not have symptoms suggesting CNS disease.)

***Additionally, for individuals eligible to participate in the Phase II Cohort C (CNS cohort)***

31. The subject must have received no more than 3 prior chemotherapy regimens for locally advanced or metastatic disease.
32. The subject must have had at least one prior hormone-based therapy for locally advanced, recurrent, or metastatic disease.
33. Subjects must have evaluable disease. (Subjects with either measurable or non-measurable disease are eligible.)

### 8.3.2 Exclusion Criteria

*Individuals who meet any of the following exclusion criteria will not be eligible to participate in either the Phase I or Phase II part of the study:*

1. Subjects with a prior or concurrent malignancy whose natural history or treatment may interfere with the safety or efficacy assessment of the investigational regimen as determined by the investigator.
2. Subjects with known impaired cardiac function or clinically significant cardiac disease such as ventricular arrhythmia requiring therapy, congestive heart failure (New York Heart Association Functional Classification Class 2B-4) and uncontrolled hypertension (defined as systolic blood pressure > 150 mm Hg and/or diastolic blood pressure > 100 mm Hg on anti-hypertensive medications).
3. Subjects with myocardial infarction or unstable angina within 6 months prior to the first administration of study drug.
4. Subject with a history of cerebral vascular disease within 6 months prior to the first administration of study drug.
5. Subject has an active infection that requires antimicrobial therapy.
6. Subject has a history of leptomeningeal disease or spinal cord compression.
7. Subject has a history of allergic reactions attributed to compounds of similar chemical composition to OP-1250.
8. Subject has a history of a pulmonary embolism or deep venous thrombosis within the last 6 months or subject has an increased risk of thrombosis as determined by the investigator. (Subjects on chronic anticoagulation are allowed).
9. Medical history or ongoing gastrointestinal disorders that could affect absorption of OP-1250 (such as active inflammatory bowel disease, chronic diarrhea, short bowel syndrome, or major upper GI surgery including gastric resection and including difficulties with swallowing capsules).
10. Subjects requiring therapy with strong CYP3A4 inhibitors and inducers.
11. Subjects requiring medications with known risk of QT interval prolongation or increased risk of Torsades de Pointes.
12. Subject has a known HIV infection.
13. Subject has a known clinically significant history of liver disease consistent with

Child-Pugh Class B or C, including active viral or other hepatitis (eg, hepatitis B or hepatitis C virus), current alcohol abuse, or cirrhosis.

14. Subject has clinically significant co-morbidities, such as uncontrolled pulmonary disease, CNS metastases that require treatment or steroid doses of > 2 mg, active infection, psychiatric disease, or any other condition that could impact the ability of the subject to participate in this study or otherwise has the potential to confound the study results.

### 8.3.3 Removal of Subjects from Treatment or Assessment

Subjects may withdraw their consent to participate in this study at any time without prejudice. The investigator must withdraw from the study any subject who requests to be withdrawn. A subject's participation in the study may be discontinued at any time at the discretion of the investigator and in accordance with his/her clinical judgment. When possible, the tests and evaluations listed for the EOT visit ([Table 1](#)) should be carried out.

Olema Pharmaceuticals must be notified of all subject withdrawals as soon as possible. Olema Pharmaceuticals also reserves the right to discontinue the study at any time for either clinical or administrative reasons and to discontinue participation by an individual investigator or site for poor enrollment or noncompliance.

Reasons for which the investigator or Olema Pharmaceuticals may withdraw a subject from study treatment include, but are not limited to, the following:

- Subject experiences disease progression by RECIST criteria (see [Appendix E](#)) (elevation in tumor markers in the absence of increased tumor measurements or clear clinical deterioration is not categorized as disease progression).
- Subject experiences unacceptable toxicity, ie,:
  - Subject develops unacceptable toxicity that does not resolve within the parameters defined in [Section 8.10, Table 8](#).
  - Subject experiences toxicity that is determined by the investigator to be no longer safe for the subject to continue therapy.
- Subject requests to withdraw from the study treatment.
- Subject requires or has taken medication prohibited by the protocol.
- Subject is unwilling or unable to comply with the study requirements.
- Subject was erroneously admitted into the study or does not meet entry criteria.
- Subject is lost to follow-up.
- Subject becomes pregnant.

If a subject does not return for scheduled visits, a documented effort must be made to determine the reason. If the subject cannot be reached by telephone after 2 attempts, a certified letter should be sent to the subject (or the subject's legally authorized representative,

if appropriate) requesting contact with the investigator. This information should be recorded in the study records.

Prior to enrollment into the study, the investigator or designee must explain to each subject, that the subject's protected health information obtained during the study may be shared with the study sponsor, regulatory agencies, and Institutional Review Board (IRB)/Ethics Committee (EC) in order to analyze and evaluate study results. It is the investigator's (or designee's) responsibility to obtain written permission to use protected health information per country-specific regulations, such as Health Insurance Portability and Accountability Act (HIPAA) from each subject, or if appropriate, the subject's legally authorized representative. If permission to use protected health information is withdrawn, it is the investigator's responsibility to obtain a written request, to ensure that no further data will be collected from the subject and the subject will be removed from the study.

